The effects of a personalized sleep improvement App from SleepScore Labs: a single-blinded randomized waitlist controlled trial

Title	The effects of a personalized sleep improvement App from SleepScore Labs: a single-blinded randomized waitlist controlled trial
Protocol version identifier	Apr 28, 2023 (replaces previous version from Jan 26, 2023)
Product	SleepScore Labs App commercially distributed for measuring sleep and providing sleep advice based on a dynamic and personalized advice engine.
Sponsor	ResMed Germany Inc., [name]
Research question and objectives	
Primary objective:
 
 - To assess changes in subjective sleep quality measured using validated questionnaires (SF-B) between active sleep-improvement condition through the Dein Schlaf. Dein Tag. App and waitlist condition after 6 weeks and 12 weeks 
Secondary objectives:
 
 - To assess changes in further metrics between app condition and waitlist condition comparing baseline with 6 weeks and 12 weeks follow-up including feeling of being refreshed in the morning, overall sleep complaints, and health measures using validated questionnaires (PSQI, PSS, SF-12, SF-B). Within the app condition, six objective sleep parameters (sleep onset latency, wake after sleep onset, total sleep time, sleep efficiency, sleep staging, nighttime awakenings) will be assessed by comparing baseline with 6 weeks and 12 weeks follow-up.
Country of study	Germany
Author	
 • [name] (Principal Investigator) • [name] (Primary SSL) • [name] (Primary ResMed) • [name] (Secondary ResMed)

Marketing authorisation holder(s)

Marketing authorisation holder(s)	Legal representative in Europe: ResMed Germany Inc., [name] [contact] [contact]
--	---

1. Table of contents

1. Table of contents	3
2. List of abbreviations	5
2.1 Declaration of Helsinki and Signatures	6
3. Abstract	7
4. Amendments and updates	9
5. Milestones	10
6. Rationale and background	11
7. Research question and objectives	12
8. Intensity of Use	12
9. Research methods	12
9.1 Study design	12
9.2 Randomization and allocation concealment	13
9.3 Blinding	13
9.4 Type/Design of study	13
9.4.1 CONSORT Study Flow Diagram	14
9.4.2 Primary Endpoint	14
9.4.3 Secondary Endpoints	15
9.4.4 Study population	15
9.4.5 Study duration	16

2.1 Declaration of Helsinki and Signatures

The undersigned have read this protocol and agreed to conduct this study in accordance with all stipulations of the protocol and in accordance with the Declaration of Helsinki.

Date

[figure not shown]
Name and Signature

[name] (Applied Sleep Scientist, SleepScore Labs)

[name] (Director Medical Affairs CRS, ResMed)

[name] (Senior Manager Medical Affairs CRS, ResMed)

09.05.2023

[name] (Univ.-[name]. med., Principal Investigator)

3. Abstract

Title	The effects of a personalized sleep improvement App from SleepScore Labs: a single-blinded randomized waitlist controlled trial
Rationale and Background	The Dein Schlaf. Dein Tag. sleep improvement App powered by SleepScore has not yet been empirically validated in the long-term assessment and management of people in the general population suffering from sleep complaints but did not yet fulfill the clinical criteria of an insomnia disorder.
Research objectives	
Primary objective: Assessed at baseline, 6 weeks and 12 weeks, improvements in self-reported sleep quality while using a dynamic and personalized sleep advice engine app will be compared to a waitlist control group.
 
Secondary objectives: Assessed at baseline, 6 weeks and 12 weeks, improvements in mental health, sleep problems, and stress will be compared to a waitlist control group. In the intervention (app) group, changes in objectively measured sleep parameters (sleep onset latency, wake after sleep onset, total sleep time, sleep staging, nighttime awakenings) over 6 and 12 weeks will be studied .

Study design	Single-blinded randomized waitlist controlled trial
Population	
Inclusion criteria:
 
 ▪ iOS user, or user of one of the following: Samsung Galaxy S7 Edge and S7, S8, S8+, S9, S9+, S20, S20 FE, S20+, S21 Ultra Samsung Galaxy Note 8 and 9 ▪ Regensburg Insomnia Scale (subclinical insomnia: Score 13-24) ▪ ≥ 18 years old. ▪ Naive to the SleepScore Labs App ▪ Able to fully understand information on data protection and provide written informed consent ▪ Not included in other treatments targeting sleep 
Exclusion criteria:
 
 ▪ Clinically significant sleep disorders (e.g. Restless legs disorders, sleep-related breathing disorders, parasomnias) ▪ Bedtime less than 6 hours ▪ Any of the following medical problems:

	
 ○ Current mental disorder affecting sleep (e.g., depression, anxiety disorders, bipolar disorder, schizophrenia) ○ Current severe medical conditions (e.g. chronic pain, cancer) ▪ Any of the following medications/substance use: 
 ○ Prescription of sleep medication or over-the-counter sleep medication (e.g., melatonin, "Hoggar night") ○ Medication for other conditions (e.g., anxiety, ADHD) that affect sleep, e.g., antidepressants, antipsychotics. ○ Consumption of 3+ units of alcohol on 4 or more nights per week ○ Recreational drug use ▪ Pregnant or nursing mothers ▪ Infant or child under age 1 at home ▪ Shift work ▪ Current use of other Sleep Tracking App's
Variables	
Questionnaire data will be collected at baseline, after 6 and 12 weeks.
 
Objective sleep data will be collected using the SleepScore App, and stored within the Microsoft Azure cloud system, an ISO 27001 certified and SOC 1 and SOC 2 compliant cloud service provider. Self-reported questionnaire data will be captured using an EU data center of Forsta/Decipher which is GDPR compliant, ISO 27001 certified, with SOC2 accredited data centers.

Data sources	
Data obtained from users: Baseline, 6-weeks, and 12-weeks measurements derived from validated questionnaires
 
Data imported from the Dein Schlaf. Dein Tag. App: Objective sleep data, daily logging, and usage monitoring data recorded by the Dein Schlaf. Dein Tag. App

Study size	
Overall, 600 users (300 app condition, 300 waitlist control group) will be included in Germany.

Data analysis	
The questionnaire data will be analyzed by an ANOVA, with one factor (app condition vs. waiting list control group) and time (Baseline, 6-weeks, 12-weeks). To handle missing values, a mixed-model approach with the same factors will be applied. The

	
critical statistical test would be the interaction term between app condition and the waiting-list control group.
 
Objectively measured data will be analyzed using multi-level modeling (MLM) in a nested way (nights within participants), allowing for analyzing changes within the intervention (app) group. To evaluate changes in primary and secondary outcome measures assessed by validated scales at baseline, 6-weeks, and 12-weeks, we will compare within-group differences for each time-point using a t-test if normally distributed, or the Mann Whitney-U test for non-normally distributed continuous data. In addition, effect sizes for the changes within both groups (questionnaire data) and app group (objective sleep parameters) will be computed.

--	---

4. Amendments and updates

Amendment No. 1, Jan 26 2023

Amendment No. 2, Apr 28 2023

Section	Amendment or update detail	Reason
5 Milestones	Dates changed	Adapted according to preparation of study
9.4 Design	Deleted “written”, added “A participant information document with consent form will be provided with page-turning function. Participant has to agree that his/her data will be used in this study by clicking “yes, I agree” or “no I don’t agree and do not want to participate”.”	Electronic consent ensures that participants can follow a defined workflow and pathway and will be guided smoothly through the recruitment portal. This avoids that too many potential participants are being lost during the course of recruitment.
9.4.1	Adapted flowchart: Informed Consent – then baseline assessment – then randomization	Now follows the routine in study practice. Before the randomization should have occurred before the baseline assessment. Since randomization means access to the app for the “app group”, the timepoint of filling out the baseline questionnaire could have been after first app usage. This will be avoided when doing baseline before randomization and app download.
9.5.1 Data	Deleted Munich Chronotype Questionnaire	Conversion into electronic format problematic; would have compromised the outcomes

9.5.1 Data	Deleted Landecker Inventar zur Erfassung von Schlafstörungen (LISST)	Study flow and assessment of participants for eligibility in the e-portal required a combination of in-/exclusion criteria with the LISST to ensure all screening criteria could be met. LISST is not required to be applied as a separate questionnaire.
9.7.1 Data management	Deleted [...],“forwarded to SleepScore, there combined with objectively measured sleep data, and then securely shared with ResMed where it will be stored for 10 years.” Added: “Objective sleep data from the app as collected and controlled by SleepScore Labs and self-reported questionnaire data as collected by a vendor on behalf of ResMed Objective sleep data from the Dein Schlaf. Dein Tag. App as specified in this protocol, and without personal identifiers will be send to vendor, combined with self-reported questionnaire data by vendor and equipped with new identifiers to result in a de-identified set of study data. [...]shared with Sleepscore Labs for joint analysis.” Added: “De-identified study data will be stored at ResMed for 10 years.”	Changes were necessary to be compliant with EU-GDPR. Processes had to be restructured to prevent ResMed from potentially getting access to personal data of study participants.
Annex 1	Deleted LISST	Not required as separate questionnaire. Accurate recruitment of participants through automated electronic assessment made a fusion of eligibility criteria necessary.
Annex 1	Deleted Munich Chronotype Questionnaire	Conversion into electronic format problematic; would have compromised the outcomes
Inclusion criteria	Added “Samsung Galaxy S7 Edge and S7, S8, S8+, S9, S9+, S20, S20 FE, S20+, S21 Ultra Samsung Galaxy Note 8 and 9”	Increasing the number of active users of the application by also allowing other devices which have been validated to deliver a similar performance in running the app.

5. Milestones

Milestone	Planned date
Start of enrolment	January 2023 (actual)
End of enrolment	May 2023 (anticipated)
Final results	July/August 2023 (anticipated)

6. Rationale and background

Sleep disturbances have a documented impact on general mental and physical well-being across many domains (e.g., Cappuccio et al., 2010; Dinges et al., 1997; Knutson et al., 2007). It has been estimated that approximately 20-35% of individuals report moderate symptoms of poor sleep (Hillman and Lack, 2013). Sleep-wake dysfunction contributes to the pathogenesis and evolution of neuropsychiatric conditions including depression, anxiety, and chronic pain, and are associated with an increased risk of chronic neurological health conditions including cerebrovascular disease, cardiovascular disease and neurodegenerative disorders. Those with poor sleep may experience general dissatisfaction with sleep quality or quantity which may be associated with minor to moderate difficulty initiating or maintaining adequate sleep (Benca et al., 2005).

The cause of sleep-wake dysfunction may be attributed to a myriad of environmental (e.g., excessive bright light before sleep), cognitive (e.g., pre-sleep worrying and anxiety), behavioral (e.g., caffeine or alcohol consumption prior to sleep), and physiological factors (e.g., pre-sleep arousal). A variety of sleep improvement options exist for poor sleep including pharmacological interventions, over-the-counter sleep aids, and cognitive and behavioral interventions. While the preferred treatment for those with clinical threshold poor sleep is cognitive behavioral therapy for insomnia (CBT-i) delivered in person, this effective approach is both time-consuming and costly, with implementation limited by an unmet need for trained providers (Espie et al., 2001). Furthermore, studies suggest that many individuals with sleep difficulties do not seek professional help and report a preference for non-pharmacological and personalized, self-help strategies (Vincent and Lionber, 2001, Morin et al., 2006). Despite this, few evidenced-based sleep improvement digital programs exist founded on the principles of behavioral change psychology and sleep hygiene targeting non-clinical populations for primary prevention.

Due to poor sleep's multitude of causes (e.g., environmental, cognitive, behavioral, or physiological) and symptoms (e.g., long sleep onset latency, short sleep duration, elevated wake after sleep onset and nighttime awakenings, poor sleep quality), a personalized and dynamic sleep improvement program tailored to a user's lifestyle and specific needs may be required to help nudge users towards sleep-promoting behaviors and attitudes. Digital and mobile health platforms are also highly scalable and cost-effective, thus allowing for widespread implementation across larger populations.

The purpose of the present study is to conduct a randomized controlled trial to evaluate a digital smartphone application, the Dein Schlaf. Dein Tag. application powered by SleepScore, designed to improve sleep and sleep-permissive behaviors. The Dein Schlaf. Dein Tag smartphone application utilizes a dynamic and personalized sleep advice engine founded in the principles of behavior change psychology and sleep hygiene that offers a novel, non-invasive and non-pharmacological solution designed to improve sleep

outcomes in those with common sleeping difficulties. While the sleep measurement technology behind Dein Schlaf. Dein Tag. has already been previously validated against gold-standard polysomnography (Zaffaroni et al., 2019), its sleep improvement features have not yet been empirically validated in the long-term assessment and management of people in the general population with a broader range of sleep problems.

7. Research question and objectives

The primary objective of the present study is to examine improvement regarding self-reported sleep quality when using the Dein Schlaf. Dein Tag. sleep improvement engine App when compared to a waitlist condition. Validated questionnaires will be administered to assess self-reported sleep quality, health perception, psychosocial factors and sleep-permissive behaviors (i.e., preventative health).

Due to the dynamic and personalized nature of the intervention and its potential impact on various sleep-wake parameters depending on the user's objectively measured sleep (only app condition) and self-assessed goals, we have chosen multiple secondary endpoints: sleep onset latency, wake after sleep onset and total sleep time will be used to determine sleep changes.

Participants will be required to complete the following tasks during the study period:

1. Start the sleep tracking device via a smartphone app before lying down in bed and turning off the lights to go to sleep (only for intervention (app) group).
2. In the morning, turn off the sleep tracking device as soon as they wake up and decide to leave the bed (only for intervention (app) group).
3. Log day and regularly use the different modules addressing different aspects of sleep, including advice for change (only for intervention (app) group).
4. At the three time points shown in 8.4.1 flow diagram, complete a longer questionnaire using an E-Link. These questionnaires will cover demographic information, subjective mental and physical health, subjective sleep, and stress level. (valid for app condition and waitlist control group)

8. Intensity of Use

Although app condition participants will be instructed to track sleep and engage with the app every night, the minimal internal compliance threshold for intensity of use is set at 3 nights of tracking per week. If participants track less than 3 nights per week, they will receive up to 3 reminder follow-up emails. The primary analysis will include all randomized participants. Secondary analyses will be conducted using an adherent to treatment approach, excluding participants who did not sufficiently engage with app throughout the study (<3 tracked nights of sleep per week).

9. Research methods

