4.3 Violations of the protocol

Participants in the app condition who do not track their sleep for 3 nights or more per week will be excluded from parts of the secondary analyses.

5 Variables

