6.1 Missing values

Missing values will not be replaced. All available data will be used for analyses. For further details see sections 7 and 8 on statistical methods and analyses.

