6.2 Outliers

The analyses comprise all measured and documented values. Excluded are only those values that have been identified or confirmed by an investigator to be a measurement error or a confirmed false entry, e.g. typos in the date of birth.

7 Statistical methods

Demographic and other key study variables will be compared between intervention group and control group at the baseline using t tests for continuous variables and chi squared for categorical variables to test whether the randomization has worked adequately.

The questionnaire data will be analyzed by an ANOVA, with one factor (app condition vs. waitlist control group) and time (Baseline, 6-weeks, 12-weeks). To handle missing values, a mixed-model approach with the same factors will be applied. The critical statistical test would be the interaction term between app condition and the waitlist control group.

For objectively recorded sleep data, repeated measured data will be analyzed using multi-level modeling (MLM) in a nested way (nights within participants), will be performed allowing for analyzing changes with the intervention (app) group. To evaluate changes in primary and secondary outcome measures assessed by validated scales at baseline, 6-weeks, and 12-weeks, we will compare within-group differences for each time-point using a t-test if normally distributed, or the Mann Whitney-U test for non-normally distributed continuous data. In addition, effect sizes for the changes within both groups (questionnaire data) and app group (objective sleep parameters) will be computed.

8 Statistical analyses

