8.2 Secondary analyses

The sleep quality SQ component of the SF-B will be calculated similar to the primary analysis, but using a per-protocol approach (participants who are adherent to treatment), excluding participants who did not sufficiently engage with app throughout the study (<3 tracked nights of sleep per week, as averaged over the entire follow-up period, respectively used the app modules regularly).

The GES component of the SF-B (feeling of being refreshed after sleep), the physiological and psychological component of the SF-12, the total score of the Pittsburgh Sleep Quality Index questionnaire (PSQI) and the score of the perceived stress scale PSS will be tested for significant changes between app condition and control condition at baseline, at 6 weeks and at 12 weeks. This will be done with the paired t-test, if there are no significant deviations from a normal distribution, otherwise the Wilcoxon matched pairs test will be used.

Objective sleep parameters (sleep onset latency, wake after sleep onset, total sleep time, sleep efficiency, sleep stages, nighttime awakenings) will be tested for significant change in the app condition comparing baseline with data at 6 and 12 weeks of follow-up.

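### The objective-sleep model names no weekday/weekend term, so a change in which nights users record could be counted as a change in sleep

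*Protocol*

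**What the plan says.** The model for the recorded sleep data is given three times in nearly the same terms: in the protocol Abstract ("Objectively measured data will be analyzed using multi-level modeling (MLM) in a nested way (nights within participants"), in protocol 9.8, and in SAP 7 ("repeated measured data will be analyzed using multi-level modeling (MLM) in a nested way (nights within participants"). All three give the nesting. None lists fixed effects, random slopes or the coding of time, and neither document defines the baseline nights or the 6- and 12-week windows.

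SAP 8.2 tests six objective parameters for change from baseline to 6 and 12 weeks in the app condition. The waitlist arm has no recordings.

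On which nights enter, protocol section 8 says "app condition participants will be instructed to track sleep and engage with the app every night", and also that "the minimal internal compliance threshold for intensity of use is set at 3 nights of tracking per week". SAP 8.2 defines insufficient use as "<3 tracked nights of sleep per week, as averaged over the entire follow-up period", so single weeks may fall below three. SAP 4.3 says that participants below the threshold "will be excluded from parts of the secondary analyses", without saying whether the multilevel model is one of those parts. SAP 6.1 adds: "Missing values will not be replaced. All available data will be used for analyses".

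**The concern.** Nesting nights within participants removes stable differences between people. It does not remove a change over time in which of one person's nights are recorded. Users start each recording themselves. If they record most nights at the start and later let weekend nights lapse more than work nights, or the reverse, the baseline and follow-up windows hold different kinds of night.

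In a randomised comparison a shift common to both arms would cancel. Here there is no second arm, so the shift passes straight into the estimated change. At stake is whether a significant change in total sleep time, latency, efficiency or another recorded parameter reflects sleep or recording habits. If weekday nights are the ones that lapse and weekend sleep is longer, the artefact looks like a benefit in total sleep time.

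**Working it through.** The documents state no figure for this effect, so there is none to reproduce. What follows is a sensitivity calculation.

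**Inputs from the documents.** 300 app users (protocol 9.6); a floor of 3 tracked nights per week (protocol 8); available nights only (SAP 6.1); app-arm contrast only (SAP 8.2).

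**Assumptions, not in the documents.** Weekend minus weekday difference in total sleep time, D = 30 to 60 min; night SD 60 min; person SD 45 min; SD of person-level change 25 min; no true change; one-week windows; all 300 users retained; 85% of all nights recorded at baseline.

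**Step 1: how far the mix can move.** Of *k* recorded nights in a week, the weekend share can range as follows.

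| Nights recorded | Weekend share |
|---|---|
| 7 | fixed at 2/7 |
| 6 | 1/6 to 1/3 |
| 5 | 0 to 2/5 |
| 4 | 0 to 1/2 |
| 3 | 0 to 2/3 |

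Full tracking fixes the mix; tracking at the floor leaves it almost free.

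**Step 2: formula.** Spurious change = D × (weekend share at follow-up − weekend share at baseline). With recording probabilities *a* on weekdays and *b* at weekends, nights per week = 5a + 2b and weekend share = 2b/(5a + 2b). Equal probabilities at baseline give 2/7 = 28.6%.

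**Step 3: artefact.** For a = 0.50, b = 0.30, the share is 0.6/3.1 = 19.4%, a change of −0.092. For D = 30, 45 and 60 this gives −2.8, −4.1 and −5.5 min.

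**Step 4: false rejection.** The standard error follows from variance = [25² + 60² × (1/n₀ + 1/n₁)]/300, where n₀ = 5.95 and n₁ is nights per week at follow-up. At n₁ = 3.1 this is 2.8 min; simulation, which allows for varying night counts, gives 2.9. At 2.9, the chance that a two-sided 5% test rejects is about 16%, 30% and 48%.

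| Follow-up recording (weekday / weekend) | Nights per week | Weekend share | Artefact, D = 30 / 60 (min) | False rejection, D = 30 / 60 |
|---|---|---|---|---|
| 0.85 / 0.85 | 5.95 | 28.6% | 0 / 0 | 5% / 5% |
| 0.70 / 0.60 | 4.70 | 25.5% | −0.9 / −1.8 | 6% / 11% |
| 0.60 / 0.50 | 4.00 | 25.0% | −1.1 / −2.1 | 7% / 13% |
| 0.50 / 0.30 | 3.10 | 19.4% | −2.8 / −5.5 | 16% / 48% |

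The two middle rows use their own standard errors (about 2.6 and 2.7 min). Simulating the last row (600 data sets per scenario) gave 18%, 28% and 50% for D = 30, 45 and 60, in line with the closed form.

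**Step 5: other settings.** With 150 users instead of 300, the 18%, 28% and 50% become about 11%, 18% and 28%. With six-week windows the artefact is about the same but the standard error falls to 1.8 min, and simulated rejection rises to 36% (D = 30) and 65% (D = 45). If weekday nights lapse instead, the sign reverses: about +3.4 min at D = 30 in one simulated case.

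**Step 6: with a weekend indicator.** The same simulations give a bias near zero, rejection of 4% to 6% and an unchanged standard error of 2.9 min. A separate simulation with other assumed SDs (40 min between and 60 min within participants, three nights per window), with the weekend share rising by 0.20, gave mean estimates of 0.5 min (D = 30) and 0.0 min (D = 60) with the term included. Without it, the artefacts were 6.0 and 12.0 min.

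**The case against.** Much of the opposing case stands.

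- **The model is unspecified, not mis-specified.** No terms are listed, so the plan has not rejected a weekend term. That is correct, and the wider gap is the missing model terms and windows. But a model fitted as written has no protection, and a term chosen after seeing the data would be discretionary.
- **The harm needs two facts.** It takes both a weekend/weekday difference and a changing mix, and the documents give neither. A reader might infer that sparse tracking alone biases the result, or that these p-values do reflect tracking habits. Neither follows: sparse tracking with a stable mix gives no bias.
- **The 3-night floor is not the schedule.** The instruction is to track every night, supported by reminder emails and app prompts (protocol 8 and 9.4.9) and a payment for regular use (protocol 9.4.7). The floor permits a shift in mix but does not cause one, and it is not said to define the data set for this model.
- **The larger figures come from severe scenarios.** They put the average user at about 3.1 nights per week, down from 5.95. The milder rows of the table are just as compatible with the documents.
- **Only total sleep time was worked through.** Latency, wake time, efficiency, staging and awakenings have no figure here.
- **A date does not identify a free day.** No work calendar is collected, so leave, public holidays and part-time work would be misclassified. Shift workers are excluded, which makes a calendar proxy more reasonable, but it remains a proxy.

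**Conclusion.** The point holds as a conditional weakness in a secondary analysis. The plan names no night-type term for an uncontrolled before-after comparison on self-selected nights, and its adherence rule leaves room for the night mix to move. If weekend sleep differs and the mix shifts, the change estimate is biased by the product of the two.

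Under the stated assumptions the size runs from nothing (stable mix), through about −1 to −2 min and 6% to 13% false rejection (mild differential drop-off), to about −3 to −6 min and 16% to 50% (share falling from 29% to 19%). The direction could equally be positive.

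A reader might go further and conclude that the objective results are invalid, or that the trial's main result is in doubt. The documents support neither. They do not show that a shift will occur, and the primary SF-B sleep quality comparison uses questionnaires from both randomised arms and does not depend on which nights are recorded. Adding the term would also leave these tests uncontrolled; it removes one source of bias only.

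**What to change.** In SAP 7, for all objective parameters:

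1. Add a fixed effect for night type to the multilevel model, derived from the recording date: Friday or Saturday night versus other nights, as a proxy for free nights.
2. Report baseline, 6-week and 12-week means standardised to a fixed 5:2 weekday:weekend mix.
3. Tabulate the number and day-of-week mix of recorded nights per window, so that readers can see whether the mix moved. This requires the windows to be defined.

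The cost is a few sentences and one derived variable. SAP 8.4 says that tracked nights are monitored daily, so no new data should be needed, and the simulations showed no loss of precision. There are two small drawbacks: the calendar proxy misclassifies some free nights, and the term assumes that the weekend effect is constant over the study, which may not hold if the app itself makes bedtimes more regular.
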